1.2. Study Design

Study GPHM is a Phase 3, multicenter, randomized, parallel-arm, placebo-controlled, double-blinded, 84-week study that will investigate the effects of treatment with the MTD of tirzepatide (10 mg or 15 mg QW) compared with placebo on body weight management of study participants who have obesity (BMI ≥ 30 kg/m²), or are overweight (BMI ≥ 27 kg/m²) with at least 1 weight-related comorbid condition, and achieved $\geq 5\%$ weight reduction after a 12-week lead-in period with an intensive lifestyle modification program.

Study GPHM will consist of 4 periods:

- a 2-week screening period
- a 12-week lead-in period during which participants undertake an intensive lifestyle modification program to achieve $\geq 5\%$ body weight reduction
- a 72-week, double-blind, placebo-controlled treatment period (including a 20-week dose escalation period), and
- a 4-week safety follow-up period.

Study participants who achieve at least 5% weight reduction will be randomized in a 1:1 ratio (tirzepatide MTD QW or placebo) at the end of the lead-in period. An upper limit of 70% enrollment of women will be used to ensure a sufficiently large sample of men.

[figure not shown]

Figure GPHM.1.1. Illustration of study design for Clinical Protocol I8F-MC-GPHM.

The details about the overview of study periods and study visits can be found in the GPHM Protocol Section 4. The details of the unique visits not displayed in [Figure GPHM.1.1](#) are provided below.

Visit 99

Visit 99 is only applicable to participants who discontinue the study treatment prematurely (between Visit 10 and Visit 28) and decline to complete the remaining scheduled study visits. These participants will be asked to return for Visit 99 at 72 weeks \pm 7 days after randomization. This visit is critical to ensure complete data collection for the primary endpoint.

Early Discontinuation of Treatment Visit

Participants unable or unwilling to continue the study intensive lifestyle intervention (during the lead-in period), or study drug intervention (during treatment period) for any reason, will perform an early discontinuation (ED) of treatment visit. If the participant is discontinuing during an unscheduled visit or a scheduled visit, that visit should be performed as the ED visit.

2. Statistical Hypotheses

The alternative hypothesis (H) for the primary objective is the following:

[figure not shown]
- H1 - QW tirzepatide MTD is superior to placebo for mean percent change in body weight AND the proportion of participants who achieve $\geq 5\%$ body weight reduction from randomization to 72 weeks.
 - The above hypothesis will be tested at 2-sided significance level of 0.05.

The alternative hypotheses for the key secondary objectives controlling for type 1 error rate are the following:

- H2 - QW tirzepatide MTD is superior to placebo for the proportion of participants who maintain $\geq 80\%$ of the body weight lost during the 12-week lead-in period (per evaluation at 72 weeks).
- H3 - QW tirzepatide MTD is superior to placebo for the proportion of participants who achieve $\geq 10\%$ body weight reduction from randomization to 72 weeks.
- H4 - QW tirzepatide MTD is superior to placebo for the proportion of participants who achieve $\geq 15\%$ body weight reduction from randomization to 72 weeks.
- H5 - QW tirzepatide MTD is superior to placebo for the proportion of participants who achieve $\geq 20\%$ body weight reduction from randomization to 72 weeks.
- H6 - QW tirzepatide MTD is superior to placebo for the mean change in waist circumference (cm) from randomization to 72 weeks.

2.1. Multiplicity Adjustment

For primary and key secondary efficacy objectives, the details of type I error control strategy are illustrated in [Figure GPHM.2.1](#). Both efficacy estimand and treatment regimen estimand will be used to assess those objectives. As they are intended for different purposes, no multiplicity adjustments will be made for conducting separate analyses relative to the efficacy and treatment regimen estimands. In addition, no multiplicity adjustments will be made for evaluating other secondary and exploratory objectives and safety assessments.

Abbreviation: H = hypothesis.

Figure GPHM.2.1. Type 1 error control strategy for primary and key secondary efficacy endpoints.

3. Analysis Sets

For purposes of analysis, the following populations are defined.

Table GPHM.3.1. Description of Analysis Datasets

Population	Description
Entered	All participants who sign informed consent
Enrolled	All participants who are enrolled in the 12-week lead-in period
Randomized	All participants who are randomly assigned a study drug
Modified Intent-to-Treat (mITT)	All randomly assigned participants who are exposed to at least 1 dose of study drug. Participants will be included in the treatment group to which they were randomized.
Efficacy Analysis Set (EAS)	Data obtained during the double-blind treatment period from the mITT population, excluding data after discontinuation of study drug (last dose date + 7 days)
Full Analysis Set (FAS)	Data obtained during the treatment period from the mITT population, regardless of adherence to study drug
Safety Analysis Set (SS)	Data obtained during the treatment plus follow-up period from the mITT population, regardless of adherence to study drug

Note: Unless otherwise specified, for analyses guided by the treatment regimen estimand, the FAS will be used. For analyses guided by the efficacy estimand, the EAS will be used, and for safety analysis, the SS will be used.

4. Statistical Analyses

4.1. General Considerations

Statistical analysis of this study will be the responsibility of Eli Lilly and Company (Lilly) or its designee. Some analyses and summaries described in this analysis plan may not be conducted if not warranted by data (for example, few events to justify conducting an analysis). Additional analyses of the data may be conducted as deemed appropriate.

Unless otherwise noted, all tests of treatment effects will be conducted at a 2-sided alpha level of 0.05, and the confidence interval (CI) will be calculated at 95%, 2-sided.

Unless specified otherwise, efficacy and safety will be assessed using the modified intent-to-treat (mITT) population, and data will be analyzed based on the assigned treatment (that is, not the actual treatment received by the participant). For submission to the US FDA to support the registration of tirzepatide for chronic weight management, the primary efficacy analysis will be conducted using the Full Analysis Set (FAS). For other purposes, the efficacy analysis of the double-blind period will be conducted using the Efficacy Analysis Set (EAS). Safety analysis of the double-blind period will be conducted using the Safety Analysis Set (SS).

Unless otherwise specified, for analyses in the double-blind period, baseline is defined as the last nonmissing data collected prior to or at randomization (prior to the first dosing of study drug). For analyses in the lead-in period, baseline is defined as the start of screening and ends prior to the intensive lifestyle modification program (typically at Week -12).

Summary statistics for continuous measures will include sample size, mean, standard deviation (SD), median, minimum, and maximum. The analysis model to make comparisons among treatment groups relative to continuous measurements assessed over time will be either analysis of covariance (ANCOVA) or an MMRM, with terms of treatment, visit, treatment-by-visit interaction, stratification factors, and corresponding baseline measurement as a covariate. An unstructured covariance structure will model the relationship of within-patient errors.

The Kaplan-Meier method will be used for estimation of cumulative event-free survival rates over time, and Cox proportional hazards regression analysis will be used to compare hazard rates among treatments.

Summary statistics for categorical measures (including categorized continuous measures) will include sample size, frequency, and percentages. Logistic regression will be used to examine the treatment difference in binary efficacy outcomes if there is a need to adjust for covariates. Otherwise, Fisher's exact test will be used to examine the treatment difference in categorical outcomes.

Summary statistics for discrete count measures will include sample size, mean, SD, median, minimum, and maximum.

For some specific safety-related parameters, the definition of baseline and postbaseline for the double-blind period is specified in [Table GPHM.4.1](#).

The definition of baseline and postbaseline during the intensive lifestyle modification lead-in period can be found in Appendix 4 (Section [6.4](#)).

Table GPHM.4.1. Baseline and Postbaseline Definitions for Safety Groups

Analysis Set	Analysis Type	Baseline	Postbaseline
SS	1.1) Treatment-emergent adverse events	The baseline period is defined as ongoing at the time of the first dose of study drug in the double-blind treatment period.	Starts after the first dose of study treatment and ends at the end of the study period (including off-drug follow-up visit)
SS	1.2) Treatment-emergent abnormal labs ^a , vital signs, and ECGs	The last nonmissing assessment (scheduled or unscheduled) recorded at or prior to randomization to the double-blind treatment period	Postbaseline will be defined as measurements after the randomization visit. All scheduled and unscheduled measurements will be included.
SS	1.3) Change from last baseline to Week xx and to last postbaseline for labs ^a , vital signs, and ECGs	The last nonmissing assessment (scheduled or unscheduled) recorded during the 12-week lead-in period	Postbaseline will be defined as above (1.2). Only scheduled visits will be included. The early discontinuation visits are considered scheduled visits.

Abbreviations: ECG = electrocardiogram; SS = Safety Analysis Set.

^a Immunogenicity-related analysis is specified in Section 4.6.5.6.

For the primary and key secondary efficacy endpoint analyses subject to type 1 error rate control, data for participants with missing values at the 72-week visit will be imputed based on the method described in Section 4.3.2.3. Otherwise, missing values will not be explicitly imputed except for the parameters with only 1 postbaseline measure during the analysis period per the schedule of activity, where the last-observation-carried-forward (LOCF) approach will be applied to impute the endpoint when ED measure is available.

End of study participation for a participant will be the earliest of date of death, date of withdrawal from further participation in the study, or date of safety follow-up visit (Visit 801). For participants considered to be lost to follow-up, end of study participation will be the date of lost to follow-up reported by the investigator. Participant data included in the database after the last date of study participation will be excluded from statistical analysis.

Statistical summaries and results of statistical analyses will be displayed in the following order: Placebo, tirzepatide MTD.

Not all analyses described in this SAP will necessarily be included in the clinical study reports (CSRs). Any analysis described in this SAP and not provided in the CSR would be available upon request. Not all displays will necessarily be created as a “static” display. Some may be incorporated into interactive display tools instead of or in addition to a static display.

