**4.1.1.3. *Safety Follow-Up Period******Visit 801***

All randomized participants are required to complete a safety follow-up visit (Visit 801), according to the SoA. Participants discontinuing the study drug early and performing an ED visit will also be asked to perform the safety follow-up visit (see Section 7.2). During the safety follow-up period, participants will not receive study drug. Participants are also required to return any remaining study diaries to the study site at the end of this period.

Visit 801 (safety follow-up visit) should be performed 4 weeks after the last visit in the treatment period (Visit 28 or Visit 99) or 4 weeks after the ED visit for randomized participants who decline to return for Visit 99.

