## **8.9. Immunogenicity Assessments**

Where local regulations and ERBs allow, blood samples for immunogenicity testing will be collected to determine antibody production against tirzepatide as specified in the SoA (Section 1.3).

For immunogenicity testing, venous blood samples will be collected from each participant according to the SoA (Section 1.3) to determine antibody production against tirzepatide. To interpret the results of immunogenicity, a PK sample will be collected at the same time points as the immunogenicity sample. All samples for immunogenicity should be taken predose when applicable and possible.

In the event of systemic drug hypersensitivity reactions (immediate or nonimmediate), additional unscheduled samples will be collected as detailed in Section 8.3.2.7 (Hypersensitivity Reactions).

Instructions for the collection and handling of blood samples will be provided by the sponsor. The actual date and time (24-hour clock time) of each sampling will be recorded. Samples collected at Visit 801 will assess immunogenicity at washout of tirzepatide (5 half-lives post end of treatment).

Immunogenicity will be assessed by a validated assay designed to detect ADAs in the presence of tirzepatide at a laboratory approved by the sponsor. Antibodies may be further characterized for their ability to neutralize the activity of tirzepatide on GIP and GLP-1 receptors. Positive tirzepatide ADA samples will be tested for cross-reactivity with native GIP and GLP-1, and, if positive, may then be tested for neutralizing antibodies against native GIP and/or GLP-1. In vivo laboratory indicators for effect on weight loss and PK will be utilized to detect potential neutralizing effect of ADA against tirzepatide.

Treatment-emergent ADAs are defined in Section 9.4.6.

Samples will be retained for a maximum of 15 years after the last participant visit, or for a shorter period if local regulations and ERBs allow, at a facility selected by the sponsor. The duration allows the sponsor to respond to future regulatory requests related to tirzepatide. Any samples remaining after 15 years will be destroyed.

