4.6. Safety Analyses

Unless specified otherwise, safety assessments for the double-blind period will be based on the SS (Table GPHM.3.1). All data collected between randomization and the end date of study participation will be included, regardless of the adherence to study drug.

Safety outcomes during the intensity lifestyle modification lead-in period will also be summarized for all enrolled participants. Detailed analyses can be found in Appendix 4 (Section 6.4).

The statistical assessment of homogeneity of the distribution of categorical safety responses between tirzepatide and placebo will be conducted using Fisher's exact test, unless specified otherwise.

The mean change from baseline differences among treatments at all scheduled visits will be assessed via an MMRM using REML. Unless specified otherwise, if the safety parameter is assessed at 72 weeks, then the model will include country/pooled country, sex, percentage of body weight reduction at the end of lead-in ($<10\%$ and $\geq 10\%$), treatment group, visit, and treatment-by-visit interaction as fixed effects and baseline value of the safety parameter as a covariate. To model the covariance structure within participants, the unstructured covariance matrix will be used. If this model fails to converge, the covariance structures specified in Section 4.3.2.2 will be tested in order until convergence is met. If the data do not warrant the MMRM model, then an ANCOVA model will be conducted.

For selected parameters, time-to-first-event analysis via the Cox proportional hazards model may be conducted. Participants without the event will be censored at the end of study participation.

For participants experiencing the event, the “time-to-first-event” will be the time (in weeks) from first dose to first occurrence of the event.

Where necessary, the rate of events will be analyzed using a generalized linear mixed model, assuming the number of events follows a negative binomial distribution, with treatment as a fixed effect. The logarithm of days during the active treatment period will be adjusted as an offset, to account for possible unequal treatment duration of follow-up between participants.

Unless otherwise specified, all the analyses listed in this section will be conducted using up to 72 weeks treatment period, plus the safety follow-up (Visit 801), for all randomized participants.

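### As written, the SAP's last-postbaseline change for labs, vital signs and ECGs takes the off-drug Visit 801 value for most to all participants

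*SAP*

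**What the plan says.** SAP 4.1, Table GPHM.4.1, row 1.3 covers the change from last baseline to a given week "and to last postbaseline for labs", vital signs and ECGs. Its postbaseline cell reads: "Postbaseline will be defined as above (1.2). Only scheduled visits will be included. The early discontinuation visits are considered scheduled visits".

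The row 1.2 definition that it borrows reads: "Postbaseline will be defined as measurements after the randomization visit. All scheduled and unscheduled measurements will be included". Neither row states where the window closes.

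Row 1.3 is assigned to the Safety Analysis Set (SS), which SAP Section 3, Table GPHM.3.1, defines as "Data obtained during the treatment plus follow-up period from the mITT population, regardless of adherence to study drug". SAP 4.6 adds a default: unless otherwise specified, its analyses "will be conducted using up to 72 weeks treatment period, plus the safety follow-up (Visit 801), for all randomized participants".

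On Visit 801 itself, Protocol 4.1.1.3 states: "During the safety follow-up period, participants will not receive study drug". Protocol 8.9 describes its timing: "Samples collected at Visit 801 will assess immunogenicity at washout of tirzepatide (5 half-lives post end of treatment".

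**The concern.** A last-postbaseline change is normally read as where participants stood at the end of treatment. Row 1.3 places no limit on the window, and a scheduled off-drug visit follows the treatment period, so a programmer applying the text would pick that visit. For someone who completed 72 weeks on drug, the Week 72 measurement would be replaced by one taken after washout. Any laboratory, pulse or ECG change that recedes when drug is stopped would then look smaller in this summary than it was on treatment. The label would not tell the reader so.

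**Working it through.** The documents give no figure for this point, such as expected Visit 801 attendance, so there is nothing to reproduce. The check is a trace of the rule, followed by a bound on how many participants it affects.

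**1. Does the window reach Visit 801?**
- Row 1.3 takes the row 1.2 window, which is everything after the randomization visit, and keeps only scheduled visits.
- Row 1.2 governs treatment-emergent abnormal values. SAP 4.6.3.4 and 4.6.3.5 count such vital signs and ECG values over the entire study, expressly including the off-drug follow-up. The borrowed window therefore does extend to Visit 801 where it is used.
- The SS and the SAP 4.6 default point the same way. Nothing in SAP 4.6.3.4 to 4.6.3.6 removes Visit 801 from last postbaseline.

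**2. Is Visit 801 scheduled, and are these measures taken there?**
- It is a column of the Schedule of Activities. Protocol 4.1.1.3 requires it of all randomized participants, 4 weeks after Visit 28 or Visit 99, or 4 weeks after the early discontinuation (ED) visit if Visit 99 is declined.
- The rows for vital signs, insulin, calcitonin, pancreatic amylase and lipase carry marks at Visit 28, ED and 801.
- The ECG, hematology, chemistry and lipid rows also end in three marks, but their columns do not align cleanly in the text version. Protocol 4.1.1.2.3 lists no ECG or laboratory work at Visit 99, so these marks are read as Visit 28, ED and 801.

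**3. Which value does row 1.3 select?**

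| Participant | Last scheduled treatment-period value | Row 1.3 as written |
|---|---|---|
| Completes treatment, attends 801 | Visit 28, on treatment | Visit 801, washout |
| Stops drug, stays to Visit 28, attends 801 | Visit 28, already off drug | Visit 801, 4 weeks later |
| Stops drug, returns only for Visits 99 and 801 | ED or last scheduled visit | Visit 801 |
| Stops drug, declines Visit 99, attends 801 | ED | Visit 801, 4 weeks after ED |
| Does not attend 801 | Last scheduled visit or ED | Same value |

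**4. How many participants?** Let d be dropout (0.25, from the sample size sections of both documents) and a the Visit 801 attendance among dropouts (not given; assumed 0 to 1). If all non-dropouts attend, the share ending on Visit 801 is (1 − d) + d × a. With 600 randomized:
- a = 0: 0.75 + 0 = 75%, or 450 of 600
- a = 0.5: 0.75 + 0.125 = 87.5%, or 525 of 600
- a = 1: 0.75 + 0.25 = 100%, or 600 of 600

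If only 90% of non-dropouts attended (assumed), the range would be 0.75 × 0.90 = 67.5% to 67.5% + 25% = 92.5%.

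**5. How far off drug?** At the protocol's 5 half-lives, 2^(−5) = 3.1% of drug remains. As a cross-check, inclusion criterion 4 equates 5 half-lives plus 90 days with 4 months, so 5 half-lives is about 30 days and one half-life about 6 days. Visit 801, 28 to 35 days after the last weekly dose, then leaves 2^(−28/6) = 3.9% to 2^(−35/6) = 1.8%. These are drug levels, not effect sizes.

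**The case against.** The strongest reply is that little rests on this row. SAP 4.6.3.4 to 4.6.3.6 summarize vital signs, ECGs and labs by planned or nominal visit. Treatment differences in pulse, heart rate and PR interval use the repeated-measures model of SAP 4.6. Pancreatic enzymes have their own repeated-measures model in SAP 4.6.5.1.1. No operative section builds a treatment comparison on last postbaseline. This stands. A reader might infer that the trial's end-of-treatment safety results are lost or understated, and the documents do not support that.

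A reader might also put a number on the dilution, for example by assuming an on-drug pulse effect and scaling it by residual exposure. The documents give neither an effect size nor a rate of reversal, so any such number would only restate its assumptions.

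The sponsor may have meant a treatment-period endpoint. Row 1.1 names the off-drug follow-up visit and row 1.3 does not, Table GPHM.4.1 is introduced as covering the double-blind period, and the clause counting ED visits as scheduled does little if Visit 801 usually displaces them. That intent is plausible, but the text does not state it. SAP 4.6 describes its safety assessments as those of the double-blind period and still includes data to the end of study participation, so that label does not exclude Visit 801.

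Finally, Protocol 9.4.4 sets a safety estimand irrespective of adherence, so off-drug values are expected. This justifies keeping values from participants who stopped drug within the 72 weeks. It does not make a visit at which everyone is off drug by design an end-of-treatment measurement. Protocol 4.2 assigns that period to the effects of drug cessation. The estimand does rule out one tempting remedy, which is to prefer the ED value over later scheduled visits.

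**Conclusion.** The point holds for one planned summary. Under the text as written, row 1.3 last postbaseline is Visit 801 for 75% to 100% of participants. That range rests on the documents' 25% dropout, an assumed 0% to 100% attendance among dropouts, and attendance by all others. A claim that nearly every participant is affected goes beyond what the documents show.

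The replacement of an on-treatment value by a washout value mainly concerns treatment completers. Early stoppers who stay to Week 72 are already off drug at that visit, so a reader should not attribute their long off-drug interval to Visit 801.

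The direction of any bias, for effects that reverse on stopping, is toward no difference, and its size is unknown. No confirmatory result depends on it, and Week 72 remains available by visit. It is a low-stakes defect, worth correcting because the correction is nearly free.

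**What to change.** In SAP Table GPHM.4.1, row 1.3, define last postbaseline as the last scheduled value in the 72-week treatment period, through Visit 28. Use the ED visit only when no later scheduled treatment-period value exists, which keeps the irrespective-of-adherence estimand. Report Visit 801 as a separate follow-up row. Leave row 1.2 unchanged, since values at any time should still run through Visit 801.

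The cost is a short wording change and one extra display row, with no new data.

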### **7.3. Lost to Follow up**

A participant will be considered lost to follow-up if he or she repeatedly fails to return for scheduled visits and is unable to be contacted by the study site. Site personnel or designee are expected to make diligent attempts to contact participants who fail to return for a scheduled visit or were otherwise unable to be followed-up by the site.

Site personnel, or an independent third party, will attempt to collect the vital status of the participant within legal and ethical boundaries for all participants enrolled, including those who did not get IP. Public sources may be searched for vital status information. If vital status is determined to be deceased, this will be documented, and the participant will not be considered lost to follow-up.

Lilly personnel will not be involved in any attempts to collect vital status information.

Discontinuation of specific sites or of the study as a whole are handled as part of Section 10.1 (Appendix 1).

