#### **9.4.4. Safety Analyses**

Unless specified otherwise, safety assessments will be guided by an estimand comparing the safety of tirzepatide MTD with placebo irrespective of adherence to study drug. Thus, safety analyses will be conducted using SS.

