4.6.3. Additional Safety Assessments

4.6.3.1. Deaths

A listing of all deaths during the study will be provided. The listing will include participant identification including the treatment, site number, participant number, date of death, age at the time of enrollment, sex, cause of death as reported by investigator, cause of death as adjudicated by the Clinical Evaluation Committee (CEC), and so on.

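### The SAP cut-off at end of participation makes no exception for deaths, so deaths found after a formal withdrawal or an early Visit 801 drop out of the by-arm safety summaries

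*SAP*

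**What the plan says.** SAP 4.1 sets the end of participation at whichever comes first of death, withdrawal from further participation, or Visit 801. For participants considered lost to follow-up, "end of study participation will be the date of lost to follow-up reported by the investigator". It then closes the window: "Participant data included in the database after the last date of study participation will be excluded from statistical analysis". SAP 4.6 takes safety data for the double-blind period from randomization to that same end date. SAP 4.6.4 limits notable events for narratives, deaths included, to the period ending at the same point.

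On ascertainment, Protocol 7.3 says that the site or someone outside it "will attempt to collect the vital status of the participant within legal and ethical boundaries for all participants enrolled". Public sources may be searched. A participant found to have died is no longer classed as lost to follow-up.

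On the timing of Visit 801, Protocol 4.1.1.3 places it four weeks after Visit 28 or Visit 99, "or 4 weeks after the ED visit for randomized participants who decline to return for Visit 99".

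On reporting, SAP 4.6.3.1 says: "A listing of all deaths during the study will be provided". Deaths are also counted by treatment in the AE overview (SAP 4.6.2.1), in adjudicated cardiovascular death (SAP 4.6.5.8) and in the registry output (SAP 6.5).

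**The concern.** Because the end date is the earliest of three dates, a death cannot displace a withdrawal or Visit 801 that came before it. The protocol makes an effort to learn of such deaths, and the SAP then applies a general rule that sets them aside. Dropping later laboratory values or non-fatal events after someone leaves is ordinary practice, since those are observed only by chance. Death differs: its date can be established without the participant attending, and a count by randomized arm over the planned period is what a reader expects.

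At stake is the completeness of a very small count. With few deaths in the trial, a single one in or out can alter how the overview table reads, and the decision should not be left to how a programmer reads a general exclusion.

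**Working it through.** **Which deaths are affected.** Take three participants, each of whom stops taking part at about Week 20 and dies at Week 30. Planned observation from randomization is 72 + 4 = 76 weeks.

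| Participant | End of participation under SAP 4.1 | Death at Week 30 |
|---|---|---|
| Formally withdraws at Week 20 | Week 20 (withdrawal) | Excluded from summaries |
| Stops drug, ED visit at Week 20, declines Visit 99, Visit 801 at Week 24 | Week 24 (Visit 801) | Excluded from summaries |
| Contact lost at Week 20, no withdrawal, no Visit 801, later found dead | Week 30 (death), since Protocol 7.3 removes the lost-to-follow-up status | Kept |

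The third result depends on reading Protocol 7.3 together with SAP 4.1. The SAP does not itself say that the end date is reset.

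Formal withdrawal is not confined to people who refuse further contact. Protocol 7.2 also covers withdrawal at the investigator's discretion, because of pregnancy, or because another obesity treatment is needed. Vital status could still be lawfully sought for some of these participants.

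**How many deaths.** The documents give no mortality figure and no withdrawal rate, so this is a range on stated assumptions.

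- Randomized: 600 (SAP section 5).
- Early leavers: at most 600 × 0.25 = 150. The 25% is the dropout figure used for power (SAP section 5), not a withdrawal rate, so it serves only as a ceiling.
- Share of leavers in the two affected groups: 25% to 100% (assumed).
- Time after exit: 38 weeks on average, half of 76, if exits are spread evenly (assumed).
- Mortality: 0.1% to 0.5% per year, the same in leavers and stayers (assumed).
- 52.18 weeks per year.

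Expected deaths after the cut-off = 150 × share × (38 / 52.18) × mortality.

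- Low: 150 × 0.25 × 38 / 52.18 = 27.3 person-years; × 0.001 = 0.03 deaths.
- High: 150 × 1.00 × 38 / 52.18 = 109.2 person-years; × 0.005 = 0.55 deaths.
- Ceiling, if all 76 weeks fell after exit: 150 × 76 / 52.18 × 0.005 = 1.1 deaths.

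Treating the count as Poisson, the chance of at least one affected death is 1 − exp(−0.0273) ≈ 3% at the low end and 1 − exp(−0.546) ≈ 42% at the high end.

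**Against the whole trial.** Planned follow-up is 600 × 76 / 52.18 = 873.9 person-years, giving 0.9 deaths at 0.1% per year and 4.4 at 0.5%. The share of person-time beyond the cut-off is 27.3 / 873.9 = 3.1% to 109.2 / 873.9 = 12.5%. These figures assume that every such death would be found. Incomplete searches lower them.

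**The case against.** The other side has real points.

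- *The group is narrow.* Protocol 7.2 says that stopping drug, including for an adverse event, is not a valid reason to leave the study. It also says that participants who agree to give endpoint information at the end are not counted as discontinued. This stands, and it is why the size above is a ceiling.
- *The death listing may already cover these deaths.* SAP 4.6.3.1 promises all deaths during the study, Protocol 4.4 runs the study to the last participant's last visit, and a listing is arguably not a statistical analysis. That reading is possible but is not stated. It would also leave the AE overview, adjudicated cardiovascular death and the narratives untouched.
- *The deaths are still reported.* Protocol 8.3.1 has SAEs learned of after participation sent promptly to the sponsor. That serves pharmacovigilance; it does not place them in the by-arm tables.
- *The data may be patchy.* Protocol 7.3 promises only an attempt, within legal and ethical limits. The Schedule of Activities has no vital-status item, and late SAEs go on a paper form. Protocol 7.2 restricts use of information after consent to disclosure is withdrawn. All of this stands and shapes the fix.

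Three stronger readings are tempting, and the documents do not support them. A reader might infer that deaths in everyone who leaves early are discarded; Protocol 7.3 rescues those who would otherwise be lost to follow-up. A reader might see a breach of Protocol 9.4.4, where "safety assessments will be guided by an estimand comparing the safety of tirzepatide MTD with placebo irrespective of adherence to study drug"; that wording concerns adherence to drug, and SAP 4.6 honours it up to the end of participation. A reader might also suppose that early leavers mostly go because of adverse events, or that the loss will fall unequally by arm. Neither document says so.

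**Conclusion.** The gap is real but limited to two groups: participants who formally withdrew, and participants who declined Visit 99 and so had Visit 801 early. For them a known death within the planned 76 weeks is removed from the by-arm summaries and the narratives by a stated rule. Its place in the death listing is undefined.

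The expected number is well under one to about one death, on assumed mortality and leaving rates that the documents do not supply. That is small in absolute terms but not negligible beside roughly one to four deaths in the whole trial on the same rates. No power, alpha or efficacy result is affected, and deaths are not part of the multiplicity-controlled testing. The change is worth making because it is cheap and settles the matter in advance.

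**What to change.** Add to SAP 4.1, in substance:

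- The exclusion of data after end of participation does not apply to deaths. Any death dated within 76 weeks of randomization, and lawfully obtained within the participant's consent, is counted in the randomized arm in the AE overview and the death listing. Where the data allow, it is also counted in adjudicated cardiovascular death and the registry tables.
- Such a death is flagged if it falls after the end of participation, and the count is also shown without flagged deaths.
- A participant first classed as lost to follow-up and later found dead has the date of death as end of participation.
- Censoring of all other events is unchanged.

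The cost is a few lines in the SAP, one flag, and a check that vital-status findings and late paper SAE reports reach the analysis database, which the documents do not confirm. The downside is that deaths found by search may lack cause or adjudication detail, and ascertainment may vary between countries with local law and public records. That is the reason for showing the count both ways.
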